3.1. Trial design

REAGIR is a multi-site, individually randomized, placebo-controlled trial. Patients presenting to one of the Aravind Eye Hospitals in India or to the University of California, San Francisco (UCSF) will be eligible for inclusion if they meet eligibility criteria (SAP section 5.2).

Enrolled participants will be randomized with equal probability (1:1) to one of two groups:

- **Sham RB-PDT:** Chlorhexidine gluconate, 0.02% (acanthamoeba), moxifloxacin 0.5% (smear/culture negative) or natamycin 5% (fungal keratitis) plus sham RB-PDT

- **RB-PDT**: Chlorhexidine gluconate, 0.02% (acanthamoeba), moxifloxacin 0.5% (smear/culture negative) or natamycin 5% (fungal keratitis) plus RB-PDT

Study participants will be required to have 8 visits: enrollment/baseline (Day 0), Day 1 (visit window: Day 1 or Day 2) for further assessments and to begin study drug, Day 2 for the cross-linking procedure within 48 hours of enrollment, and follow-up visits at 3 days, 3 weeks (visit window: 2.5 – 5 weeks), 3 months (visit window: 2.5 -3.5 months), 6 months (visit window: 5-7 months) and 12 months (visit window: 10-14 months). Additional visits may be needed and will be determined by the physician/investigator.

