3.2. Randomization

Randomization will be stratified by site. Stratified, block randomization will ensure that an approximately equal number of patients are randomized to each treatment group by site. The exact block size will be randomly permuted (e.g., block size of 4 with probability 0.7 and 6 with probability 0.3) with block sizes and their probabilities known only to the biostatistician.

Once an eye is in the study enrolled (only one eye can be enrolled from each patient), the study coordinator will assign the study participant's eye an ID (alpha-numeric code) and organize the procedure in the operating room within 48 hours of enrollment. Once the study participant has been assigned a study participant ID and randomized to treatment arm, they will be included in the intent to treat analysis.

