6.2. Analysis methods

Primary Outcome

Visual Acuity at 6 months. We will use a multiple linear regression model to estimate the mean difference between groups in BSCVA measured in logMAR at 6 months. The model will include covariates for treatment arm (a binary indicator variable for RB-PDT), indicators for study site (randomization strata), and baseline pinhole visual acuity. We propose a two-sided alpha of 0.05 for the primary analysis.

For study participants who experience perforation or the need for TPK this will be noted and BSCVA will be recorded prior to performing surgery (either corneal glue or TPK). These study participants actual 6-month visual acuity will be used in the primary analysis. As a sensitivity analysis, the last observation (at 3 weeks or 3 months) will be carried forward (LOCF) as the 6-month BSCVA.

The measurement window for the 6-month primary BSCVA outcome will be 5-9 months. The window was chosen after examining the distribution of measurement timing in masked data. As a sensitivity analysis, we will include all participants, including those who had their primary outcome measured out-of-window.

A supplementary analysis using linear mixed effects regression will be conducted to analyze all BSCVA data (including 3-week and 3-month observations). The model will include baseline BSCVA and treatment assignment as covariates (fixed effects) plus a random effect for patient to allow for repeated measures over time. Such analyses will be sharply distinguished from the primary pre-specified analysis. Permutation testing will be the basis of inference. Specifically, we will conduct 10,000 random permutations of treatment assignment, and conduct the primary regression analysis on these re-randomized data sets. We will then compare the observed regression coefficients to the randomization distribution, reporting the quantiles.

In all analyses, model adequacy will be checked by examination of residuals or other goodness of fit tests as needed. Inadequate model fit will prompt us to report alternative models. If there are chance imbalances in prognostic baseline patient characteristics, a secondary analysis will include them as covariates in the regression model.

Secondary Outcomes

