Visual Acuity at 3 weeks, 3 months, and 12 months. We will compare BSCVA between arms at 3 weeks, 3 months, and 12 months follow-up using the same approach as the primary analysis. We will only complete this analysis after the primary analysis is complete and the trial is unmasked.

Scar/infiltrate. The analysis for scar/infiltrate size will follow the templates for visual acuity given

above. Multiple linear regression models will be used to evaluate 3-week, 3-month, 6-month, and 12-month scar size by treatment arm while correcting for baseline measurements. Corneal thinning and scarring will be evaluated similarly using Anterior Segment Optical Coherence Tomography (AS-OCT) correcting for baseline values.

Corneal Perforation. A Cox proportional hazards model will estimate the hazard of perforation, defined as perforation (flat anterior chamber with presence of iris plugging a defect in the cornea or seidel positivity) or the need for TPK while correcting for baseline infiltrate depth.

Microbiological cure. We will re-culture all study participants at Day 2, prior to starting antibiotics to assess the effect of RB-PDT on rate of microbiological cure. We hypothesize that those in the RB-PDT group (Arm 2) will have a higher rate of microbiological cure on 2 day cultures than those randomized to the Sham group (Arm 1).

We propose the primary analysis to be a Fisher's exact test comparing the proportion of positivity at follow-up between initially culture positive individuals who were assigned to RB-PDT (Arm 1) versus initially culture positive individuals assigned to the Sham group (Arm 1).

Additionally, we will report the results for initially culture negative individuals as a supplementary analysis in a linear binomial regression with assignment, indicators for site (randomization strata), and initial culture results as covariates.

Visual Function Questionnaire (VFQ). VFQ will be compared between arms controlling for Day 1 VFQ. NEI-VFQ in the US and the Indian-VFQ (IND-VFQ) in India. This will be conducted using linear regression with baseline and treatment assignment variables.

Pain Scale. Pain is assessed at day 0, day 1, and day 3 using a 0-10 scale for patient self-assessment. Multiple linear regression models will be used to evaluate 3-day pain by treatment arm while correcting for baseline pain.

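### The perforation/TPK Cox model, the VFQ and pain regressions and the main culture test omit site, the randomization stratum: a small loss unless sites differ substantially, and a wording change repairs it

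*SAP*

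**What the plan says.** SAP 3.2: "Randomization will be stratified by site". Allocation is 1:1 (SAP 3.1). The primary BSCVA model in SAP 6.2 respects the strata; beside treatment arm its covariates are "indicators for study site (randomization strata), and baseline pinhole visual acuity".

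Some secondary analyses in SAP 6.2 inherit this. BSCVA at other visits uses the primary approach, scar/infiltrate follows the visual acuity template, and the MIC analysis follows the primary model.

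Four others do not name site:

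- **Perforation/TPK (Cox model).** The only adjustment named is depth: "the need for TPK while correcting for baseline infiltrate depth".
- **VFQ.** "This will be conducted using linear regression with baseline and treatment assignment variables". The instrument varies by country: "NEI-VFQ in the US and the Indian-VFQ (IND-VFQ) in India".
- **Pain.** The model is to "evaluate 3-day pain by treatment arm while correcting for baseline pain".
- **Culture, main test.** Fisher's exact test in initially culture-positive participants, without stratification.

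The supplementary culture regression in the same section does carry site indicators, labelled as randomization strata. Protocol 9.4.2 shows the same pattern for the Cox model, Fisher's test, the supplementary culture regression and VFQ.

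**The concern.** When allocation is balanced within strata, the analysis should account for those strata. Otherwise, if the strata are prognostic, a linear model leaves between-site variation in the residual and overstates its standard error. In a Cox model, leaving out a prognostic stratum moves the hazard ratio toward 1. The SAP follows this principle for BSCVA and gives no reason for departing from it here.

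Site could plausibly be prognostic. The antifungal for fungal ulcers is different in Brazil (Protocol 6.1.1). Surgery is at the treating physician's discretion (Protocol 6.5.1), so the TPK part of the composite can reflect local practice. The VFQ instrument differs by country.

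At stake is the precision of secondary outcomes. Fewer perforations or TPKs is a stated expectation (SAP 2.2), and perforation is among the endpoints the DSMC weighs for harm (SAP 3.5).

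**Working it through.** **1. The plan's own figure.** The only REAGIR power statement is for the primary endpoint (SAP 3.3).

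- Residual SD = 0.293 × √(1 − 0.216²) = 0.286.
- Evaluable per arm = 165 × 0.85 = 140.25.
- Standard error = 0.286 × √(2/140.25) = 0.0342.
- Power for 0.11 logMAR = Φ(0.11/0.0342 − 1.96) = 0.896, against 90% stated.

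The figure reproduces, and this point does not touch it. No power is stated for REAGIR perforation/TPK, VFQ, pain or culture.

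**2. VFQ and pain (linear models).** Let *f* be the share of residual variance due to site. With site-balanced allocation the estimate is as precise as with site in the model, but the reported standard error is too large by 1/√(1 − *f*). The effective critical value becomes 1.960/√(1 − *f*). Where the model with site has 80% power, the noncentrality is 1.960 + 0.842 = 2.802. Without site:

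- power = Φ(2.802 − 1.960/√(1 − *f*))
- type I error = 2 × [1 − Φ(1.960/√(1 − *f*))]

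| *f* (assumed) | SE too large by | Critical value | Power | Type I error |
|---|---|---|---|---|
| 0.02 | 1.0% | 1.980 | 79.4% | 0.048 |
| 0.05 | 2.6% | 2.011 | 78.5% | 0.044 |
| 0.10 | 5.4% | 2.066 | 76.9% | 0.039 |
| 0.20 | 11.8% | 2.191 | 72.9% | 0.028 |

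**3. Perforation/TPK (Cox model, simulated).** From the documents: 330 patients, site-stratified blocks of 4 or 6, 15% loss. Assumed: five sites with shares of 15% to 30%, depth log hazard ratio 0.5 per SD, event rates of 20% to 50%, and the hazard ratios below. The upper event rate is the only such figure in the documents (about 50% in an earlier fungal trial, Protocol 2.2). There were 400 to 500 runs per row.

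| True HR (events) | Site log-hazard SD | HR without / with site | Power without / with site |
|---|---|---|---|
| 0.70 (140–151) | 0 | 0.70 / 0.70 | 53% / 53% |
| | 0.3 | 0.70 / 0.70 | 54% / 53% |
| | 0.6 | 0.72 / 0.70 | 50% / 58% |
| | 1.0 | 0.76 / 0.69 | 37% / 61% |
| 0.60 (55–71) | 0 | 0.60 / 0.60 | 45% / 46% |
| | 0.3 | 0.60 / 0.60 | 43% / 42% |
| | 0.6 | 0.61 / 0.60 | 45% / 48% |
| | 1.0 | 0.64 / 0.60 | 42% / 54% |

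The Monte Carlo standard error of power is about √(0.5 × 0.5/400) = 2.5 points, so gaps of 1 to 2 points are noise. With no treatment effect, SD 1.0 and the higher event rate, rejection was 2.2% without site and 7.7% with site. The 7.7% is above nominal by more than its simulation error of about 1.1 points, so the 37% v 61% contrast gives the direction better than the exact gain.

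**4. Country differences only (simulated).** Five equal sites, true HR 0.60, depth as covariate, 15% censoring, 500 runs; all hazards assumed. With four Indian sites at 0.4 and Brazil at twice that, the results without and with site are HR 0.60 v 0.59 and power 73% v 73%. With Brazil at half, HR is 0.60 v 0.59 and power 64% v 65%. An eight-fold spread of yearly hazards across sites (0.15 to 1.2, or 12-month risks of 1 − e^−0.15 = 14% to 1 − e^−1.2 = 70%) gives HR 0.63 v 0.59 and power 65% v 75%.

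**5. Culture (simulated).** Assumed: 200 initially culture-positive patients, odds ratio 0.45, 3,000 runs. At site SD 0 / 0.3 / 0.6 / 1.0, Fisher's test has 74% / 73% / 68% / 58% power and a site-stratified Mantel-Haenszel test 79% / 78% / 75% / 71%. The gap of about 5 points at SD 0 is Fisher's own conservatism and has nothing to do with site.

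**The case against.** A reader might infer that every culture analysis ignores site, that these results will be biased, or that the trial loses a material amount of power for perforation/TPK. The documents support none of these.

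- The supplementary culture regression includes site; only Fisher's test lacks it.
- The linear treatment estimates are unbiased and their tests conservative. The Cox shift is toward the null. Neither creates a false-positive risk.
- A clear Cox loss needs strong differences between sites. By the protocol, REAGIR enrols at Aravind hospitals in one Indian state and one Brazilian centre, so country and antifungal separate one site from the rest. Step 4 shows almost no loss in that pattern. No section gives event rates, organism mix or surgical practice by site.
- Perforation/TPK sits within one of eleven secondary outcome entries, and SAP 4.1 treats secondary outcomes as corroborating evidence.
- Stratifying has a small price: strata with few events add little information, and site tables for culture may be sparse.

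All of this stands, and it limits the size of the point. It does not explain why four analyses depart from the rule the SAP applies to BSCVA. The SAP's provision to add covariates after chance imbalance would not bring site in, because stratified allocation keeps site balanced.

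**Conclusion.** The omission is real for the Cox, VFQ and pain models and for the main Fisher test. It is a minor point and an inexpensive improvement.

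For VFQ and pain the cost is about 1.5 to 3 points of power if site explains 5% to 10% of residual variance. For perforation/TPK it ranges from nothing, with weak site differences, to a hazard ratio of 0.76 instead of 0.70 and a clear power loss at a site log-hazard SD of 1.0. These sizes rest on assumed site effects, event rates and hazard ratios. No stated power or sample size changes.

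VFQ is the clearest case, because a pooled regression without site or country terms mixes questionnaires. Replacing Fisher's test is the weakest part, given possible sparse tables and that test's own conservatism.

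**What to change.** Amend SAP 6.2, and Protocol 9.4.2 to match, before unmasking:

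1. Stratify the perforation/TPK Cox model by site, keeping baseline infiltrate depth.
2. Add site indicators to the VFQ and pain regressions. For VFQ these also absorb a difference in level between instruments; a difference in scale would need separate handling.
3. Keep Fisher's test, and report beside it a site-adjusted analysis in initially culture-positive participants, for example the existing site-adjusted regression restricted to them.
4. State a pooling rule for small sites, for example by country, fixed without reference to arm.
5. Define the strata. For REAGIR, SAP 3.1 names Aravind and UCSF, while Protocol 4.1 names Aravind and UNIFESP. Reconcile the lists, and name the VFQ instrument for Brazil, which neither document gives.

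The cost is wording only. In the simulated Cox model with no site effect, stratifying cost nothing visible (53% v 53% power at HR 0.70). Fixing the choice now also removes a later choice between adjusted and unadjusted results.

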#### REAGIR

Patients presenting to one of the Aravind Eye Hospitals in India, or to the Federal University of São Paulo in Brazil (UNIFESP) with either smear or culture positive fungal or acanthamoeba keratitis or smear and culture negative corneal ulcers and moderate to severe vision loss, defined as Snellen visual acuity of 20/40 or worse, will be eligible for inclusion. Those who agree to participate will be randomized to one of two treatment groups:

Group 4, (Sham RB-PDT): chlorhexidine gluconate 0.02% (acanthamoeba), moxifloxacin 0.5% (smear/culture negative) or natamycin 5% (fungal keratitis) plus sham RB-PDT

Group 5, RB-PDT: chlorhexidine gluconate 0.02% (acanthamoeba), moxifloxacin 0.5% (smear/culture negative) or natamycin 5% (fungal keratitis) plus RB-PDT

We hypothesize that study participants randomized to RB-PDT will have improved BSCVA, achieve microbiological cure more quickly, have smaller scar sizes and lower perforation rates compared with those who receive topical antibiotic alone. The patient, physicians, microbiologist and refractionist performing the best spectacle-corrected visual acuity (BSCVA) assessment will be masked to the treatment group. Due to the nature of the intervention, the surgeon and technician performing cross-linking will not be masked. As in the SCUT II trial, an interim analysis will be performed once primary outcome data is available for one third of the patients (see REAGIR **Statistical Analysis Plan (SAP)**—**Section 3.5** for details).

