## 8 STUDY ASSESSMENTS AND PROCEDURES

### 8.1 EFFICACY ASSESSMENTS

The following masked efficacy assessments will be performed:

- **Slit lamp examination.** Performed by the treating physician.

- **Visual acuity assessment.** Both pinhole visual acuity and BSCVA/ETDRS/Mrx will be used depending on the time point. Visual acuity will be assessed only by a trained, masked optometrist to ensure proper procedures are followed across sites. See **MOP Section 4.4** for the visual acuity protocol.
- **Imaging assessments.** Non-contact imaging will be performed with HR AS-OCT, Pentacam topography, and slit lamp photography, and contact imaging with confocal microscopy. See **MOP Section 4.6** for detailed descriptions of imaging procedures. Performed by trained study staff.
- **Corneal Gram Stain and Culture.** Performed by the treating physician. See **MOP Section 4.2** for detailed description of corneal scraping procedures.
- **Visual function questionnaire (VFQ).** The National Eye Institute Visual Function Questionnaire (NEI-VFQ) and the Indian Visual Function Questionnaire (IND-VFQ) will be administered at UCSF/UM and Aravind, respectively. Both are validated questionnaires to evaluate the effect of vision on the patient's quality of life. Performed by trained study staff.

Please see the SoA in **Section 1.3** of this protocol for a detailed schedule of all study activities.

All of the above assessments, with the exception of the VFQ, will be performed during the screening process. These are standard of care procedures that the patient would receive even if they were not being screened for the study.

The masked treating physician may use the results of these assessments to change the participant's treatment in any way they deem necessary.

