**Visual Function Questionnaire (VFQ).** VFQ will be compared between groups controlling for Day 1 VFQ. NEI-VFQ in the US and the Indian-VFQ (IND-VFQ) in India. This will be conducted using linear regression with baseline and assignment variables.

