6.1. Outcome definitions

Primary Outcome:

Best spectacle-corrected visual acuity measured in logMAR, 6 month follow-up visit

Secondary Outcomes:

- Microbiological cure on repeat smear and culture at Day 2
- Interaction of minimum inhibitory concentration (MIC) and CXL on best spectacle-corrected visual acuity
- Infiltrate/scar size/depth, as measured by clinical exam, clinical photographs, Pentacam and OCT at week 3 and months 3, 6, and 12
- Adverse events including rate of perforation/need for TPK
- BSCVA at Day 1, 3 weeks, 3 months, and 12 months
- Astigmatism, higher order aberrations, topography, and densitometry as measured on Pentacam at week 3 and months 3, 6, and 12
- Corneal thickness and scar size/depth as measured by AS-OCT at week 3 and months 3, 6, and 12
- Basal nerve plexus, white blood cell count, and keratocyte density on confocal microscopy at week 3 and months 3, 6, and 12

- Visual function questionnaire (VFQ) will be compared between groups at 6 months, controlling for Day 1 VFQ
- Pain scale at baseline, Day 1, and Day 3
- Subgroup analysis of study participants receiving prior topical antimicrobial therapy

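### The VFQ regression has no site or instrument term and no common scoring although instruments differ by country, and the Brazilian REAGIR site is given no instrument.

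*SAP*

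**What the plan says.** SAP 6.1 lists the endpoint as a secondary outcome: "Visual function questionnaire (VFQ) will be compared between groups at 6 months, controlling for Day 1 VFQ". SAP 6.2 names the instruments, "NEI-VFQ in the US and the Indian-VFQ (IND-VFQ) in India", and gives the model: "This will be conducted using linear regression with baseline and treatment assignment variables". Protocol 9.4.2 matches: "This will be conducted using linear regression with baseline and assignment variables". Protocol 8.1 says that the NEI-VFQ and the IND-VFQ "will be administered at UCSF/UM and Aravind, respectively". UNIFESP does not appear there.

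The site lists differ. For REAGIR, Protocol 4.1 has "Patients presenting to one of the Aravind Eye Hospitals in India, or to the Federal University of São Paulo in Brazil (UNIFESP", with no US site. SAP 3.1 has "Patients presenting to one of the Aravind Eye Hospitals in India or to the University of California, San Francisco (UCSF", with no Brazilian site. The amendment history in Protocol 10.4 dates the addition of UNIFESP to REAGIR to 15 March 2023. The SAP's latest revision, which specified the secondary analyses, is dated 3 December 2024.

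SAP 3.2 stratifies randomization by site. In SAP 6.2, the primary visual acuity model and the supplementary culture regression both carry site indicators. The VFQ paragraph does not, and it does not refer back to the visual acuity template as the scar paragraph does.

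**The concern.** A regression coefficient takes the unit of its outcome. If scores from two questionnaires enter one model and their scales differ, the treatment coefficient is an average of effects in different points, weighted by how many patients used each instrument. Protocol section 3 wants VFQ to help judge whether a visual acuity difference matters to patients, and a coefficient without a defined unit serves that purpose poorly.

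Two further matters follow from the text. Leaving out site ignores the randomization strata and leaves any level difference between sites or instruments in the residual. And a reader cannot tell whether Brazilian REAGIR patients contribute VFQ data at all, or on which questionnaire. The Schedule of Activities has VFQ at Day 1 and 6 months without exempting any site. REAGIR II, which also enrolls at UNIFESP, has the same gap.

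**Working it through.** The documents give no VFQ effect size, SD or power, so there is no VFQ figure to reproduce. The visual acuity calculation in SAP 3.3 serves only to set the number of patients: residual SD 0.293 × √(1 − 0.216²) = 0.286, and 165 × 0.85 ≈ 140 evaluable per arm. The detectable difference is 0.286 × √(2/140) × (1.960 + 1.282) = 0.111 at 90% power and 0.096 at 80%, matching the stated 0.11 and 0.10. The illustration therefore uses 280 patients, 1:1 within site.

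Assumptions not in the documents: share p of patients on the second instrument; its level shifted by d SD at both visits; its scale k times the first; Day 1 to month 6 correlation r; true effect 0.35 SD on both instruments. The simulation used r = 0.5 and 2,000 replicates per cell.

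**1. Scale.** With arms balanced within site, the pooled coefficient, in SD units of the first instrument, is 0.35 × (1 − p + pk).

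| p | k = 0.5: formula (simulated) | k = 2: formula (simulated) |
|---|---|---|
| 5% | 0.341 (0.343) | 0.368 (0.369) |
| 10% | 0.333 (0.335) | 0.385 (0.387) |
| 30% | 0.298 (0.298) | 0.455 (0.451) |

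The largest simulated value was 0.458 (p = 30%, k = 2, plus a 2 SD shift). Adding a site indicator alone left the coefficients essentially unchanged. Standardizing within instrument plus the indicator returned about 0.35 in every cell. Power was 0.84 to 0.92 under the SAP model and 0.91 to 0.93 after standardizing. The simulation standardized with known means and SDs; estimated ones would add some noise at a small site.

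**2. Level shift.** A shift at both visits adds b = p(1 − p)d² to the variance at each visit and to their covariance. The standard error of the SAP model, relative to the same model with a site indicator, is

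√{[1 + b − (r + b)²/(1 + b)] / (1 − r²)}.

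With p = 0.2 and d = 1, b = 0.16:
- r = 0.3: (1.16 − 0.46²/1.16)/0.91 = 1.074; square root 1.036
- r = 0.5: (1.16 − 0.66²/1.16)/0.75 = 1.046; square root 1.023
- r = 0.7: (1.16 − 0.86²/1.16)/0.51 = 1.024; square root 1.012

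As a check at the extreme of the grid (p = 0.3, d = 2, r = 0.5), b = 0.84 and the formula gives 1.073; the simulated standard errors were 0.111 and 0.103.

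**3. Type I error.** With no true effect, the SAP model rejected in 3.6% to 5.8% of replicates. The Monte Carlo standard error is √(0.05 × 0.95/2000) = 0.5 percentage points, so there is no inflation. The lowest rates (3.6% to 3.8%) are in cells with a 30% share and a 2 SD shift, where the omitted strata make the test slightly conservative.

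**The case against.** The SAP never says that scores are pooled or raw. One regression is the natural reading, but fitting by country is not excluded. SAP 6.2 also promises residual checks and alternative models if fit is poor, and the Manual of Operations, which is not among these documents, may name a Brazilian instrument. VFQ is one of eleven listed secondary items and carries no power claim. These points limit the weight of the matter without closing it: a promise to react to poor fit does not prespecify how instruments are handled, and residual plots would not reliably reveal a difference in units.

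A reader might infer more than the documents support:
- **A biased or confounded arm comparison.** Randomization is blocked within site, so arms are nearly balanced within instrument, and the simulation shows no excess of false positives.
- **A mix of NEI-VFQ and IND-VFQ in REAGIR.** Under the current protocol REAGIR has no US site, and that mix belongs to SCUT II. If UNIFESP collects no VFQ, REAGIR has one instrument and no unit problem, but a site without the endpoint.
- **A standard error loss of about 8% at a 20% share and 1 SD shift**, from √(1 + 0.16) = 1.077. This ignores the Day 1 covariate, which absorbs most of the shift.
- **Effects that cancel because the instruments are scored in opposite directions.** The documents give neither instrument's direction or range.
- **A wrong common Day 1 slope.** The same questionnaire is used at both visits, and rescaling both by k leaves cov(kX, kY)/var(kX) unchanged. A product of instrument and Day 1 VFQ is not needed on that ground.

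**Conclusion.** The point holds as a matter of interpretability for a secondary endpoint, with a small loss of precision. The text settles three things: the VFQ model omits site although site is the randomization stratum, no common scoring is stated for instruments that differ by country, and UNIFESP has no named instrument while the SAP and protocol disagree on the REAGIR sites.

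The sizes are illustrations and depend on the Brazilian share, the scales and the correlation, none of which the documents give. In REAGIR the unit problem arises only if a second instrument with a different scale is in use. If VFQ is absent in Brazil, the weighting in SAP 6.3 cannot restore a site with no observed values, and the result would apply to India only. The importance is minor and the remedy nearly free.

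**What to change.** In SAP 6.2 and Protocol 9.4.2:
1. Add the site indicators to the VFQ model, as in the primary model. Since Protocol 8.1 assigns instruments by site, these also absorb level differences between instruments.
2. State the range and direction of each instrument's score, and score all in the same direction.
3. Standardize within instrument, for example by that instrument's Day 1 SD over both arms, applied to both visits. Alternatively, fit by instrument and combine the standardized effects.
4. Report the effect by instrument in points and combined in SD units.
5. In Protocol 8.1, name the UNIFESP instrument or state that VFQ is not collected there, and in that case say that the VFQ result excludes Brazil.
6. Reconcile the REAGIR site list in SAP 3.1 with Protocol 4.1.

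The cost is wording; sites already using an instrument need collect nothing new. The downside is that the combined effect is in SD units, which clinicians read less easily than points, so the results by instrument should stand beside it. The change should be dated before unmasking.
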